The study therapists will be integrated into the VA PC-MHI clinic. This integration will mean that the study therapists will be located in PC-MHI, attend PC-MHI staff meetings, and receive additional clinical and administrative supervision from the PC-MHI director (co-I [name]). Staff at the Ann Arbor PC-MHI clinic are primarily Master's-level social workers. Although PC-MHI largely treats patients referred from primary care clinics, the PC-MHI clinic is co-located, and will recruit directly from primary care for this study.

Patient sample.

Inclusion criteria. Eligible participants will be those who are prescribed 20 MEM/day or more as part of long-term OA therapy and who receive treatment at primary care clinics at the Ann Arbor VAMC. Long-term OA therapy will be defined as at least 84 days covered within the past 90 days. The Principal Investigator will use discretion when it is clear that the eligible participant is on long-term OA therapy, despite not having a prescription written exactly for at least 90 days (e.g. small breaks in therapy, or prescriptions intended to be taken consistently but at a lower frequency than written resulting in gaps between fills). When necessary, the Principal Investigator will confer with the physician co-investigators who are experts in chronic pain management (Drs. [name], [name], [name]). The criteria of prescribed OA dose of 20 MEM/day or greater was selected because patients prescribed this dose are at increased risk of overdose death.¹²

Exclusion criteria. To increase generalizability of findings, a minimal number of exclusion criteria will

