be used. These are: 1) plans to stop OAs or reduce dose to below 20 MEM/day in the next 6 months, 2) use of fentanyl, due to the difficulty in determining morphine equivalency (preliminary work indicated that less than 2% of VHA patients receiving OAs are prescribed fentanyl), 3) only opioid type used is Tramadol/Ultram because it is not subject to the long-term OA therapy informed consent process 4) prescribed or using Suboxone 5) terminal cancer, 6) acute risk for self-harm related to opioid use requiring immediate treatment (see next section), which is then likely to result in a reduction or cessation in opioid therapy, 7) moderately severe cognitive impairment (based on a validated six-item cognitive screener⁷⁶) to ensure accuracy of data, 8) pregnant women, and 9) inability to give informed consent. Participants may be included or excluded at the discretion of the Principal Investigator based on participant or study staff best interest (e.g. if participant should become physically or verbally aggressive towards study staff, or if study staff know a patient or their family personally, in order to fully ensure participant privacy).

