Randomization. Participants will be individually randomized to receive either the intervention or EUC after completing the baseline. The coordinator will supervise the randomization, which will be conducted by the analyst, using computerized block-randomization stratified by OEF/OIF/OND status in blocks of 10.

Intervention and EUC condition delivery procedures. The intervention and EUC procedures will each take approximately 30 minutes to complete, in addition to the chronic OA therapy informed consent. These sessions will take place in a private room or over the phone in a private office to ensure privacy and confidentiality. Consistent with our prior interventions, the sessions will be computer-aided to enhance fidelity. For the intervention, the therapist uses the computer aid to progress through a series of prompts, which ensures that each step of the intervention is covered and reminds therapists of specific ME tools relevant to each step. The computer aid also includes screens with suggested options/choices that can be shared with participants who have trouble generating goals, values, strengths, and tools without prompting. The EUC condition will also use a computer aid that will include a series of prompts and non-interactive visual aids related to the content of that condition. Feedback to the participants' prescribers will be given based on the protocol developed through the process described above.

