The 3-, 6-, and 12-month assessments will occur in at the Ann Arbor VAMC. In cases where this is not feasible for the participant, the research staff will arrange to meet the participant at a convenient location in the community (e.g. participant home, library), conduct the assessment by phone, or mail the assessment to participants to complete and return to the research team. In cases where the follow-up assessments are conducted via U.S. mail and a participant endorses risk (suicide or opioid, according to our protocol), research staff will make at least three attempts to reach the participant within 72 hours of receiving the survey to further assess level of risk and/or answer questions. Every mailed survey packet may include the resource brochure which includes national suicide hotlines, VA Crisis Line and mental health services. Privacy during assessments will be achieved by making sure no one can overhear the conversation. If applicable, research staff will ask the research subject to have others leave the room during interviews. The research assistant conducting follow-up will be blind to group status. Based on our prior research,^{68,69,79} we conservatively estimate that 80% of participants will be interviewed at follow-up. Techniques to ensure high retention include: gathering extensive tracking information, using reminder letters as well as contacting participants by phone, and scheduling follow-up interviews at the participants' convenience. Participants will be contacted two weeks prior to the assessment due date to schedule an appointment. Study staff will monitor primary care appointment logs for participants who have not responded to letter and phone contact and non-obtrusively approach patients in waiting areas. The 3-, 6-, and 12-month follow-up assessments will take approximately one hour to complete and participants will be given \$30 (+\$5 for a voluntary UDS) for each plus an additional \$10 to assist with travel expenses.

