Exclusion criteria: Patients will be excluded if they: 1) plans to stop OAs or reduce dose to below 20 MEM/day in the next 6 months, 2) use of fentanyl, due to the difficulty in determining morphine equivalency (preliminary work indicated that less than 2% of VHA patients receiving OAs are prescribed fentanyl), 3) only opioid type used is Tramadol/Ultram because it is not subject to the long-term OA therapy informed consent process 4) prescribed or using Suboxone, 5) terminal cancer, 6) acute risk for self-harm related to opioid use requiring

immediate treatment (see next section), which is then likely to result in a reduction or cessation in opioid therapy, 7) moderately severe cognitive impairment (based on a validated six-item cognitive screener⁷⁶) to ensure accuracy of data, 8) pregnant women, and 9) inability to give informed consent. Participants may be included or excluded at the discretion of the Principal Investigator.

Sources of Materials

Patients treated in the primary care clinic will initially be screened via medical records data and logs of the patients scheduled for appointments; this will be done using methods that have been IRB-approved and deemed HIPAA-compliant in our prior work. Screening based on medical records will include diagnoses and opioid prescribing from medical visits occurring in the prior 3 months. Research staff will then create a list of potentially eligible patients with appointments on a weekly basis. We may send a letter to those patients selected to be approached in advance of their appointment, which will briefly describe the study and provide a number to call to “opt out” of being approached.

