The electronic files, paper-and-pencil study documents, and/or audio recordings will be securely uploaded or entered to a restricted access file behind a VA firewall. Data collected via hard copy will be entered in the computer independently by trained data entry staff, and discrepancies will be corrected by a supervisor, based on source documents. The letter that will be sent with mailed surveys reminds participants not to include any identifiable information on their survey to ensure privacy and confidentiality. The quality of the data will be monitored by random inspection of the completed forms by the research coordinator or trained RA and any problems detected will be discussed with the PI. Blind interim analyses of the data will be conducted at two points - when 50 and 75% of the sample has been accrued. The PI and study data analyst will analyze the data.

VA Informatics and Computing Infrastructure (VINCI)

We may request data extracts from the VHA Corporate Data Warehouse (CDW). VINCI is a partner with the Corporate Data Warehouse and hosts all data available through CDW. As VA and VHA research progresses, large amounts of data are being collected into databases maintained by a variety of investigators, studies, and locations. Individual investigators and multiple databases may lack sufficient resources to ensure consistency and quality control, or a long-term commitment to data storage and access. Therefore, there are less consistent standards for the protection of Veterans data, data quality, and data access compared to a centralized repository. A centralized research data repository, such as the VA Informatics and Computing Infrastructure (VINCI), offers a number of important advantages: Consistent, defined, and transparent security and standards for access to data; a common point of entry for all investigators who use the data; tools for analysis and reporting; tighter and more consistent control over the standards and quality of the data included; and the ability to standardize and update terminology and format as technology and methodology improve.

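### The investigator's discretion over who is in the trial is not limited to exclusion or to the time before randomisation

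*Combined protocol and SAP*

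**What the plan says.** The discretion is stated twice, in different terms.

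- **Human Subjects, Exclusion criteria.** After nine listed exclusions: "Participants may be included or excluded at the discretion of the Principal Investigator". No ground, time limit or record of use is given.
- **Research Design and Methods, Patient sample, Exclusion criteria.** The same power with a ground: "Participants may be included or excluded at the discretion of the Principal Investigator based on participant or study staff best interest". Two examples follow. One is conduct: "if participant should become physically or verbally aggressive towards study staff". The other is that study staff know the patient or the family.

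Four other places bear on how the power could operate.

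- **Randomization.** "Participants will be individually randomized to receive either the intervention or EUC after completing the baseline". The study sessions and all follow-up contacts come later.
- **Data collection procedures.** "The research assistant conducting follow-up will be blind to group status". The investigator is not described this way. The Data Monitoring Plan says "Blind interim analyses of the data will be conducted at two points - when 50 and 75% of the sample has been accrued", which describes the analyses and not decisions about participants.
- **Patient safety.** Participants found during the study to be at serious, imminent risk of opioid-related self-harm are taken out of the study and left out of the analysis.
- **Analysis plan.** The mixed models are said to use data from all participants, including those with incomplete follow-up. No analysis set is defined as randomised, and no rule covers a participant excluded at discretion.

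**The concern.** Two separate things are at stake.

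**The population.** The power runs in both directions. A sentence that allows inclusion at discretion, placed directly after a list of exclusions, permits a listed exclusion such as fentanyl use or cognitive impairment to be set aside. The enrolled population would then not be fully defined by the stated criteria, some of which exist to protect the accuracy of the data.

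**The randomised comparison.** If the power is used after allocation, removal can depend on arm and on outcome. The intervention session explores each participant's opioid, alcohol and other drug use and overdose risk behaviours. The enhanced usual care session is didactic and leaves out overdose risk behaviours. Difficult exchanges with staff could therefore be more frequent in one arm, and the people involved could have higher risk-behaviour counts. A selective removal of that kind biases the comparison, and the planned models do not correct it if the participant's data are dropped.

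**Working it through.** **1. Reading the clauses together**

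| Question | Human Subjects | Research Design and Methods |
|---|---|---|
| Direction | include or exclude | include or exclude |
| Ground | none | best interest of participant or staff, with examples |
| Time limit | none | none |
| Reasons logged | not stated | not stated |
| Decision blind to arm | not stated | not stated |

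The example of staff who know the patient is naturally an entry matter. The aggression example is not tied to entry, since conduct can change at any contact. The Patient safety rule shows that the plan does contemplate dropping entered participants from analysis, though for a different reason and in explicit words.

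**2. The plan's own figure**

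Inputs from Power analysis: 180 per arm after 80% retention (450 × 0.80 = 360), mean count 1.9 with a Poisson distribution, incidence rate ratio (IRR) 0.80, two-sided α = 0.05.

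- Expected totals: 180 × 1.9 = 342 and 180 × 1.52 = 273.6.
- SE of log IRR = √(1/342 + 1/273.6) = 0.0811.
- |ln 0.80| / 0.0811 = 0.2231 / 0.0811 = 2.75.
- Power = Φ(2.75 − 1.96) ≈ 0.79.

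This agrees with the stated 80% to within 2 points.

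**3. Illustration of selective removal**

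Assumptions, none of them from the documents: no true effect, all removals in one arm, and a mean count of 5 among those removed. A count of 5 lies within the pilot range of 0 to 10 given under Measures.

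- 9 removed: (342 − 9 × 5) / 171 = 297 / 171 = 1.737, and 1 − 1.737/1.9 = 8.6%.
- 5 removed: (342 − 5 × 5) / 175 = 317 / 175 = 1.811, and 1 − 1.811/1.9 = 4.7%.

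For 9 removals, the chance of a false positive under the Poisson model is:

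- ln(1.737/1.9) = −0.090; SE = √(1/342 + 1/297) = 0.0793; ratio = −1.13.
- Φ(−1.96 + 1.13) + Φ(−1.96 − 1.13) ≈ 0.20, against a nominal 0.05.

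With the pilot SD of 2.0 in place of the Poisson variance:

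- SE = 2.0 × √(1/180 + 1/171) = 0.214; difference 0.163; ratio 0.76.
- The false positive rate is about 0.12.

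Varying the assumed mean to 4 or 6, and the number removed between about 4 (2%) and 9 (5%), gives Poisson false positive rates from about 0.06 to about 0.33.

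**4. What the illustration does not show**

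If the same number with the same mean left both arms, both means would fall equally and the ratio would stay at 1. Loss of power is minor: at 171 per arm, the Poisson calculation gives 0.765 in place of 0.786. The issue is bias, not sample size.

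**The case against.** The strongest reply is that removal after randomisation is an inference. Both sentences close a paragraph of exclusion criteria. Sources of Materials then describes participants who meet the criteria completing baseline and being randomised. Where the plan means removal after entry, as under Patient safety, it says so plainly. Nothing says that a participant excluded at discretion loses data already collected. This stands as far as intent goes: entry only is a plausible reading. It does not settle the matter, because neither sentence states a time and the aggression example fits later contacts.

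It is also fair that the investigator's blinding is simply not mentioned. Silence is not evidence that allocation would be used in these decisions. The size in the illustration is likewise assumed throughout.

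Two stronger readings are tempting and should not be made.

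- **That people unable to consent could be enrolled.** A reader might infer this because inability to consent is among the listed exclusions. The documents rule it out: ability to consent is an inclusion criterion under Human Subjects, the screening survey starts only after written consent, and the adverse event reporting plan requires every participant to sign before taking part.
- **That the discretion in the inclusion criteria admits patients below the dose threshold.** That clause allows for "prescriptions intended to be taken consistently but at a lower frequency than written resulting in gaps between fills", and a reader might infer that less than 20 MEM/day is in fact received. But the criterion is prescribed dose, determined from pharmacy data. The clause relaxes days covered, and only where long-term therapy is clear, with physician co-investigators consulted when needed. A test on dispensed dose would be a new criterion. If 20 MEM/day were required on average over 90 days, a patient with 83 days covered would need 20 × 90/83 = 21.7 MEM/day prescribed, which is stricter than the ordinary rule.

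**Conclusion.** The concern holds as a defect of wording with a real consequence for bias. The discretion has no limit on direction or timing, its two statements differ, and no as-randomised analysis set protects the comparison if the power is used after allocation. A reader might infer that randomised participants will be removed, or that the investigator will know the arm when deciding. The documents establish neither; they only fail to prevent it.

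The size cannot be estimated from the documents. Shifts of 4.7% and 8.6% rest on 5 or 9 removals, all from one arm, with an assumed mean count of 5. They show only that a handful of selective removals is not negligible beside a 20% design effect. The case for change rests on the text and on the low cost of closing the gap.

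**What to change.** Make the two sentences identical and state that:

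- before randomisation, the investigator may exclude an otherwise eligible patient, with the reason logged;
- the listed exclusions are not waived;
- after randomisation, a participant's study contact may be stopped, but data already collected, pharmacy outcomes and any self-report obtainable by phone or mail stay in the analysis as randomised.

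Add to the Analysis plan a definition of the primary analysis set as all randomised participants in their allocated arm.

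Reconcile this with the Patient safety section, which leaves participants at imminent risk out of the analysis. The Safety Monitoring Plan, on acute opioid-related risk, refers instead to a sensitivity analysis. When such a participant leaves study procedures is a separate clinical matter; what needs settling is whether the data are kept. Without this step the new wording would contradict the existing rule.

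For the inclusion criteria, ask the sponsor only to state how the days-covered discretion fits with the 20 MEM/day criterion.

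**Cost.** A few sentences and a short log. Some discretionary inclusions would be lost. Pharmacy extraction and phone or mail follow-up are already planned, so no new procedure is needed.

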Patient safety. During the study, we may determine that a participant is at serious, imminent risk for serious self-harm related to their OA use. Study staff will notify the participant's prescriber in this situation and will make additional referrals to mental health or emergency services as needed. These participants will be withdrawn from the study and will not be included in analysis (see section on Feedback to Providers on page 11). For non-OA related risks, such as suicidal ideation, staff will discuss the risks of participation with the patient and review screening responses and the medical chart (e.g., for ongoing mental health care) to decide study eligibility. If any of these determinations are unclear, staff will consult with the supervising psychologist ([name]) or psychiatrist ([name]), both of whom have expertise in assessing suicide risk. Participants who report acute suicidality will be able to continue with study procedures at a later time and will be referred to same-day care through either a PC-MHI-based Psychiatrist or the ED. If treatment needs are not urgent, the participant will be referred to specialty mental health and continue with study protocols. Those participants in the trial who report suicidality at a 3-, 6-, or 12-month follow-up assessment will be connected to the appropriate services (outlined in the Safety Monitoring Plan section on page 21).

Usual care, intervention, and EUC procedures. Both intervention and EUC participants will receive the Long-Term OA informed consent and will review the VHA's "Taking Opioids Responsibly for Your Safety and the Safety of Others" pamphlet with a study therapist (usual care). The study therapists will coordinate with the patients' prescribing physicians to document this process if a participant had not already provided informed consent. For the intervention condition, the informed consent process will lead to a tailored, ME-adherent discussion of reducing the risks of OAs, but for the EUC condition, the informed consent process will be followed by psychoeducation on topics related to pain management, will not be tailored, will not include elements of ME, and will not include content on overdose risk behaviors. If a patient expresses a wish to change their OA regimen after any of the intervention or control content, the study therapist will assist the patient in arranging an appointment with their prescriber.

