Intervention. The intervention session is tailored on knowledge, values, concerns, barriers, and skills/tools for managing pain. It combines elements of ME and cognitive behavioral therapy (CBT) and uses the structure of ME brief interventions. Participants are presented with a variety of risk reduction strategies, including abstinence of all substances except prescribed medications, not combining substances, and taking medications as prescribed. Participants are provided with a number of strategies for coping with pain that may reduce reliance on OAs, such as meditation, activity pacing, stretching, exercise, ice or heat, eliciting support from friends and family, and distraction. The therapist prompts the patient to reflect on which tools are likely to help him/her personally, barriers to using those tools, and plans for overcoming those barriers. The intervention does not recommend that participants stop or reduce their OA use below prescribed levels, but participants who express concern that the benefits of OAs may be outweighed by the harms are guided on how to discuss this concern with their prescriber. The session includes the following organization:

Explore: 1.) Introduce purpose of the session, affirm autonomy to make decisions; 2.) Elicit participants' strengths, values, and goals. 3.) Guide discussion of tailored behavioral history (OA use, other drug and alcohol use, overdose risk behaviors) and pain experiences using open-ended questions/probes.

Guide: 1.) Review role of cognitive factors in pain; 2.) Review risk factors for overdose, with particular emphasis on risk factors for OA overdoses, using an "elicit-provide-elicit" approach;¹⁰ 3.) Review other risks of OA use (oversedation and resulting injuries, impaired driving) and safe storage and disposal; 4.) Guide discussion of potential changes to risk behaviors and use of tools, using menus/lists, eliciting benefits of change, reflective statements, clarifying ambivalence, and anticipating and discussing barriers to change; 5.) Use confidence rulers to elicit importance, confidence, and intention to change.

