We will implement an additional notification process to the prescriber if the patient is at acute risk for self-harm. Focus groups with primary care-based OA prescribers at the study site (n=20) allowed us to understand what situations would merit a notification, how providers want to be notified and how they will use that information. The situations include, but are not limited to, using their opioid prescription along with heroin, cocaine, benzodiazepines, non-VA opioid prescription, or snorting or injecting their medication if it is not written as such. This list may change if the study team notices trends in participants that are increasing their risk of overdose and death. Any changes will be discussed and approved by the principal investigator and the clinical co-investigators (Drs. [name], [name], [name]). Providers will be notified by study staff in-person with the participant when possible, or messaged in CPRS or Lync/Skype. When messaged, a generic message will be sent to protect the participant’s privacy. Study staff will only mention the facts and not make any clinical conclusions or suggestions (e.g., only state that the participant endorsed using heroin, or tested positive for cocaine). We have developed and presented a notification plan at PACT staff meetings prior to the start of enrollment to solicit feedback and refine the plan. We anticipate that the situations that will be defined as serious, imminent risk will occur relatively infrequently.

Training protocol and assessment of fidelity. Drs. [name], [name], [name], [name] and [name] will conduct a two-day training involving a review of ME and CBT principles and techniques, the rationale for the intervention, a detailed description of the intervention, and role playing. [name] will provide training so that the therapists will be well versed in OA therapy and the evidence base for pain treatment. The study coordinator will participate in the intervention training to enhance his/her ability to monitor fidelity and contamination. The therapist hired to provide the EUC condition will have a parallel training process to learn EUC protocols. All

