Risk of contamination. There are three possibilities of contamination: (1) Contamination of the intervention with EUC. The EUC will present general educational information on pain. The potential discussion of this information by EUC participants with intervention participants should not "contaminate" the intervention condition with any information that would not normally be available. (2) Contamination of EUC with elements of the intervention. If any contamination does occur, it is expected to be minimal. Contamination of EUC with elements of the intervention will be closely monitored. Intervention therapists conducting the EUC session will be trained on strict adherence to the manual. The EUC sessions conducted by the intervention therapist will be reviewed for adherence and contamination to instruct and change before the next session. However, we will assess for changes in self-efficacy, motivation, knowledge of risk factors in all participants and will conduct ongoing fidelity assessments of EUC sessions. (3) Contamination of standard treatment. Both conditions will be provided by research staff who will not directly influence the course of treatment at Ann Arbor VAMC during the study.

Patient Advisory Committee. We will form a committee of patients from the study site. We will seek to have male and female Veterans, OIF/OEF/OND Veterans and Veterans of less recent conflicts, and Veterans with and without comorbid mental health problems on the committee. This group will be asked for advice to refine the study protocols, will meet twice yearly during active recruitment to be updated on progress and provide feedback, and will meet after data collection to provide advice for implementation.

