In the course of study participation, including the assessments, intervention, or EUC activities, it may be determined that a participant is at acute risk for serious self-harm related to their opioid use. Study staff have been trained to include in the exclusions of confidentiality, self-harm not only in terms of suicide but also related to participant's opioid prescription. Participants will be notified that research staff may discover opioid self-harm risk from the survey, intervention session or general discussion with the participant. When this risk arises, study staff will discuss this risk with the patient and discuss that the provider will be informed. The participant will be given the option to disclose this to their provider, with the study staff in the room, when possible. Study staff will notify the participant's prescriber in the situation where the participant does not, or the provider is not available, based on protocols that were designed in consultation with opioid prescribers through focus groups and primary care staff meetings. The discussion between study staff and provider will only discuss the relevant information (e.g., mentioned use of cocaine, endorsed using heroin, etc.), but will not make any clinical conclusions or suggestions. Study staff will also make additional referrals as needed. During data analysis, we examine any impact through a sensitivity analysis. Additionally, we will notify all participants' prescribers that the participant is at risk for overdose due to their medication regimen and/or OA use behaviors. The notification will include the fact that we will have discussed this risk with the patient. This will be done for both intervention and control participants to avoid potential differential effects on the measurement.

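### Acute-risk notices to prescribers can depend on arm through session disclosures, and the plan conflicts on whether notified participants are analysed, which qualifies the Aim 2 dose contrast

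*Combined protocol and SAP*

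**What the plan says.** **Where an acute notice can come from.** The Safety Monitoring Plan allows for such a finding in any study activity, "including the assessments, intervention, or EUC activities, it may be determined that a participant is at acute risk". It then has participants told that "research staff may discover opioid self-harm risk from the survey, intervention session or general discussion with the participant". The second list does not name EUC; the first does.

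**What triggers it.** Feedback to prescribers sets out the situations: "using their opioid prescription along with heroin, cocaine, benzodiazepines, non-VA opioid prescription, or snorting or injecting their medication". The list is open-ended and may be revised. These situations are expected to be fairly rare, but no rate is given.

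**What each session covers.** The Explore phase of the intervention includes the step "Guide discussion of tailored behavioral history (OA use, other drug and alcohol use, overdose risk behaviors". Usual care, intervention, and EUC procedures says the EUC session "will not include content on overdose risk behaviors".

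**What is balanced.** Feedback to prescribers and the Safety Monitoring Plan both send a routine notice to every participant's prescriber in both arms, so that it cannot act differently by arm. The acute notice is additional, and no such balancing is stated for it. Risk of contamination says: "Both conditions will be provided by research staff who will not directly influence the course of treatment".

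**How notified participants are analysed.** Patient safety withdraws participants found to be at serious, imminent opioid-related risk and leaves them out of the analysis. The Safety Monitoring Plan says of its acute-risk cases only: "During data analysis, we examine any impact through a sensitivity analysis". The Analysis plan mentions neither. Medical Chart and Administrative Data Extraction plans a chart review of the notification but links no analysis to it.

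**The concern.** Hypothesis 2a compares average prescribed dose (MEM/day) and medication possession ratio between arms, and the prescriber controls the dose. The protocol itself expects acute opioid-related risk to affect dose: exclusion criterion 6 says that such risk, when it needs immediate treatment, will probably lead to opioid therapy being reduced or stopped. If one session uncovers more of the trigger behaviours than the other, prescribers in that arm receive more acute notices, and part of any dose difference may come from those messages.

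The protocol recognises this mechanism for the routine notice and equalises it. It leaves the acute notice open, and then gives two incompatible accounts of whether the affected participants are analysed. At stake is what a lower dose in the intervention arm can be said to show. The Overdose Risk Behaviors measure counts a high dose (over 100 MEM/day) as an item, so the same route could reach Aim 1.

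**Working it through.** **Design figure.** Power analysis gives 180 analysed per arm, two-sided alpha 0.05 and 80% power at 0.30 SD for continuous outcomes including dose.
- SE of the standardised difference = sqrt(2/180) = 0.1054.
- Power = Φ(0.30/0.1054 − 1.960) = Φ(0.886) = 0.81. By t test, the effect detectable at 80% power is 0.296 SD.
- 360/0.8 = 450 randomised.

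The stated design reproduces.

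**What can depend on arm.**
- Baseline survey and urine screen: these precede randomisation (Randomization), so they are independent of arm.
- Follow-up surveys: the instruments are the same in both arms and the assessor is blind (Data collection procedures). They cover substance combinations, route of use, non-VHA opioids, and alcohol and drug use.
- Study session: a scripted behavioural history in one arm, no overdose-risk content in the other.

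Only disclosures made for the first time in a session are therefore expected to differ by arm.

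**Size if notified participants are retained.** Let e be the excess share notified in the intervention arm and c the resulting fall in their average dose, in SD. The shift is b = e × c. The documents give neither e nor the dose SD, so both inputs are assumptions. The last column is the chance of p < 0.05 when the session content itself has no effect on dose: 1 − Φ(1.960 − b/0.1054) + Φ(−1.960 − b/0.1054).

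| Excess e | Shift for c = 0.5 to 1.5 SD | Share of 0.30 SD | Chance of p < 0.05 |
|---|---|---|---|
| 2% | 0.010-0.030 SD | 3-10% | 5.1-5.9% |
| 5% | 0.025-0.075 SD | 8-25% | 5.6-11.0% |
| 10% | 0.050-0.150 SD | 17-50% | 7.6-29.6% |
| 20% | 0.100-0.300 SD | 33-100% | 15.8-81.2% |

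Example: e = 0.10 and c = 1.5 give b = 0.15 and b/SE = 1.423, so the chance is 1 − Φ(0.537) + Φ(−3.383) = 0.296. In numbers of people, 2% of 180 is about 4 and 10% is 18. Producing the whole 0.30 SD needs an excess of 30% at a 1 SD cut (0.30/1) or 20% at 1.5 SD (0.30/1.5).

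**Size if notified participants are excluded.** Removing an extra share e whose mean dose lies m SD above the arm mean lowers that arm's remaining mean by e × m/(1 − e). With m = 1 assumed:
- e = 5%: 0.05/0.95 = 0.053 SD, chance of p < 0.05 is 7.9%.
- e = 10%: 0.10/0.90 = 0.111 SD, chance 18.4%.

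Exclusion therefore changes the form of the problem without removing it. Its direction depends on the notified participants having above-average doses.

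**The case against.** The other side has several good arguments, and most of them narrow the point.

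- A reader might infer that only the intervention arm can generate these notices. The documents do not support that: EUC activities are a named source, and the same surveys and voluntary urine screens run in both arms. What stands is that only one of the two sessions is scripted to elicit the triggers.
- A reader might infer that prescriber dose cuts will certainly be counted in the Aim 2 result. Under Patient safety the later doses of serious, imminent-risk participants would not enter the analysis at all. The objection defeats the certainty, but it replaces that route with an arm-dependent exclusion.
- A reader might infer that the plan credits any dose effect to motivational style and content. The sentence in the EUC section that makes such a claim concerns overdose risk behaviour, and hypothesis 2a simply compares randomised groups. In a trial described as pragmatic, a notice prompted by the session can fairly be treated as part of the assigned strategy. This is a strong argument for keeping the randomised comparison and naming the effect accurately.
- The statement in Risk of contamination is limited to direct influence, and notices carry facts without clinical suggestions. It is not false; it just does not address this indirect route.
- Acute cases are expected to be infrequent. If so, the shift is negligible. The plan sets out no by-arm count that would show this.

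**Conclusion.** The point holds in a limited form. Ascertainment of acute risk is unequal between the two sessions, the balancing covers only the routine notice, and Patient safety and the Safety Monitoring Plan conflict on how the affected participants are analysed. Those two sections use different labels (serious, imminent risk; acute risk). Feedback to prescribers uses both for the same process without saying whether they mark the same group.

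The size cannot be established. At a 2% excess the shift is 0.01-0.03 SD and hardly matters. It becomes material at roughly a 5-10% excess or more with large dose cuts (0.05-0.15 SD at 10%). These figures rest on assumed notice rates and dose changes expressed in assumed SD units. They do not support a statement that some fixed part of the 0.30 SD design effect is artefact.

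A reader might also infer that censoring follow-up at a session-sourced notice, with inverse-probability weights, would isolate the effect of the motivational content. That does not follow. It conditions on an event that arm can affect, baseline covariates do not capture candour in the session, events may be few, and the urine screen is voluntary.

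**What to change.** Leave the safety and notification rules as they are.

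1. Reconcile Patient safety with the Safety Monitoring Plan on how these participants are analysed, and say whether the two risk labels mean the same group. For the primary Aim 1 and Aim 2 analyses, keep every randomised participant with available data, including pharmacy records, in the assigned arm.
2. Log each acute notice with its date, its source (survey, urine screen, session, conversation) and whether the trigger already appeared in the pre-randomisation survey or urine screen. Report rates by arm and source.
3. State the Aim 2 effect as that of the assigned session plus any notice it triggers, not of motivational content alone.
4. Define the promised sensitivity analysis before arms are compared. Label any version that excludes or censors notified participants as exploratory.

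The cost is a small logging burden, which the planned chart review of notifications already covers in part, and a more qualified Aim 2 conclusion. Source should be recorded at the time, because it may not be recoverable later.
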